| Adult >16 years | Asymptomatic, QTc interval 0.45 – 0.47 sec OR Increase interval <0.03 sec above baseline | Asymptomatic, QTc interval 0.48 – 0.49 sec OR Increase in interval 0.03 – 0.05 sec above baseline | Asymptomatic, QTc interval ≥ 0.50 sec OR Increase in interval ≥ 0.06 sec above baseline | Life-threatening consequences, e.g., Torsade de pointes or other associated serious ventricular dysrhythmia |
| Pediatric ≤16 years | Asymptomatic, QTc interval 0.450 – 0.464 sec | Asymptomatic, QTc interval 0.465 – 0.479 sec | Asymptomatic, QTc interval ≥0.480 sec | Life-threatening consequences, e.g. Torsade de pointes or other associated serious ventricular dysrhythmia |
| Thrombosis/embolism | NA | Deep vein thrombosis AND No intervention indicated (e.g., anticoagulation, lysis filter, invasive procedure) | Deep vein thrombosis AND Intervention indicated (e.g., anticoagulation, lysis filter, invasive procedure) | Embolic event (e.g., pulmonary embolism, life- threatening thrombus) |
| Vasovagal episode (associated with a procedure of any kind) | Present without loss of consciousness | Present with transient loss of consciousness | NA | NA |
| Ventricular dysfunction (congestive heart failure) | NA | Asymptomatic diagnostic finding AND intervention indicated | New onset with symptoms OR Worsening symptomatic congestive heart failure | Life-threatening congestive heart failure |

| PARAMETER | GRADE 1 MILD | GRADE 2 MODERATE | GRADE 3 SEVERE | GRADE 4 POTENTIALLY LIFE- THREATENING |
|---|--|--|---|---|
| GASTROINTESTINAL | | | | |
| Anorexia | Loss of appetite without decreased oral intake | Loss of appetite associated with decreased oral intake without significant weight loss | Loss of appetite associated with significant weight loss | Life-threatening consequences OR Aggressive intervention indicated [e.g., tube feeding or total parenteral nutrition (TPN)] |
| Comment: Please note that, while the grading scale provided for Unintentional Weight Loss may be used as a guideline when grading anorexia, this is not a requirement and should not be used as a substitute for clinical judgment. | | | | |
| Ascites | Asymptomatic | Symptomatic AND Intervention indicated (e.g., diuretics or therapeutic paracentesis) | Symptomatic despite intervention | Life-threatening consequences |
| Cholecystitis | NA | Symptomatic AND Medical intervention indicated | Radiologic, endoscopic, or operative intervention indicated | Life-threatening consequences (e.g., sepsis or perforation) |
| Constipation | NA | Persistent constipation requiring regular use of dietary modifications, laxatives, or enemas | Obstipation with manual evacuation indicated | Life-threatening consequences (e.g., obstruction) |

| PARAMETER | GRADE 1 MILD | GRADE 2 MODERATE | GRADE 3 SEVERE | GRADE 4 POTENTIALLY LIFE- THREATENING |
|--|--|---|--|--|
| Diarrhea | | | | |
| Adult and Pediatric ≥1 year | Transient or intermittent episodes of unformed stools OR Increase of ≤ 3 stools over baseline per 24-hour period | Persistent episodes of unformed to watery stools OR Increase of 4 – 6 stools over baseline per 24-hour period | Bloody diarrhea OR Increase of ≥ 7 stools per 24-hour period OR IV fluid replacement indicated | Life-threatening consequences (e.g., hypotensive shock) |
| Pediatric <1 year | Liquid stools (more unformed than usual) but usual number of stools | Liquid stools with increased number of stools OR Mild dehydration | Liquid stools with moderate dehydration | Liquid stools resulting in severe dehydration with aggressive rehydration indicated OR Hypotensive shock |
| Dysphagia- Odynophagia | Symptomatic but able to eat usual diet | Symptoms causing altered dietary intake without medical intervention indicated | Symptoms causing severely altered dietary intake with medical intervention indicated | Life-threatening reduction in oral intake |
| Mucositis/stomatitis (clinical exam) Indicate site (e.g., larynx, oral) See Genitourinary for Vulvovaginitis See also Dysphagia- Odynophagia and Proctitis | Erythema of the mucosa | Patchy pseudomembranes or ulcerations | Confluent pseudomembranes or ulcerations OR Mucosal bleeding with minor trauma | Tissue necrosis OR Diffuse spontaneous mucosal bleeding OR Life-threatening consequences (e.g., aspiration, choking) |
| Nausea | Transient (<24 h) or intermittent nausea with no or minimal interference with oral intake | Persistent nausea resulting in decreased oral intake for 24 – 48 h | Persistent nausea resulting in minimal oral intake for >48 h OR Aggressive rehydration indicated (e.g., IV fluids) | Life-threatening consequences (e.g., hypotensive shock) |

| PARAMETER | GRADE 1 MILD | GRADE 2 MODERATE | GRADE 3 SEVERE | GRADE 4 POTENTIALLY LIFE- THREATENING |
|--|---|--|--|--|
| Pancreatitis | NA | Symptomatic AND Hospitalization not indicated (other than emergency room visit) | Symptomatic AND Hospitalization indicated (other than emergency room visit) | Life-threatening consequences (e.g., circulatory failure, hemorrhage, sepsis) |
| Proctitis (functional-symptomatic) Also see Mucositis/stomatitis for clinical exam | Rectal discomfort AND No intervention indicated | Symptoms causing greater than minimal interference with usual social & functional activities OR Medical intervention indicated | Symptoms causing inability to perform usual social & functional activities OR Operative intervention indicated | Life-threatening consequences (e.g., perforation) |
| Vomiting | Transient or intermittent vomiting with no or minimal interference with oral intake | Frequent episodes of vomiting with no or mild dehydration | Persistent vomiting resulting in orthostatic hypotension OR Aggressive rehydration indicated (e.g., IV fluids) | Life-threatening consequences (e.g., hypotensive shock) |
| NEUROLOGIC | | | | |
| Alteration in personality-behavior or in mood (e.g., agitation, anxiety, depression, mania, psychosis) | Alteration causing no or minimal interference with usual social & functional activities | Alteration causing greater than minimal interference with usual social & functional activities | Alteration causing inability to perform usual social & functional activities | Behavior potentially harmful to self or others (e.g., suicidal and homicidal ideation or attempt, acute psychosis) OR Causing inability to perform basic self-care functions |

| PARAMETER | GRADE 1 MILD | GRADE 2 MODERATE | GRADE 3 SEVERE | GRADE 4 POTENTIALLY LIFE- THREATENING |
|---|--|--|--|--|
| Altered Mental Status For Dementia, see Cognitive and behavioral/attentional disturbance (including dementia and attention deficit disorder) | Changes causing no or minimal interference with usual social & functional activities | Mild lethargy or somnolence causing greater than minimal interference with usual social & functional activities | Confusion, memory impairment, lethargy, or somnolence causing inability to perform usual social & functional activities | Delirium OR obtundation, OR coma |
| Ataxia | Asymptomatic ataxia detectable on exam OR Minimal ataxia causing no or minimal interference with usual social & functional activities | Symptomatic ataxia causing greater than minimal interference with usual social & functional activities | Symptomatic ataxia causing inability to perform usual social & functional activities | Disabling ataxia causing inability to perform basic self-care functions |
| Cognitive and behavioral/attentional disturbance (including dementia and attention deficit disorder) | Disability causing no or minimal interference with usual social & functional activities OR Specialized resources not indicated | Disability causing greater than minimal interference with usual social & functional activities OR Specialized resources on part- time basis indicated | Disability causing inability to perform usual social & functional activities OR Specialized resources on a full- time basis indicated | Disability causing inability to perform basic self-care functions OR Institutionalizatio n indicated |
| CNS ischemia (acute) | NA | NA | Transient ischemic attack | Cerebral vascular accident (CVA, stroke) with neurological deficit |

| PARAMETER | GRADE 1 MILD | GRADE 2 MODERATE | GRADE 3 SEVERE | GRADE 4 POTENTIALLY LIFE- THREATENING |
|---|--|--|--|--|
| Developmental delay – Pediatric ≤16 years | Mild developmental delay, either motor or cognitive, as determined by comparison with a developmental screening tool appropriate for the setting | Moderate developmental delay, either motor or cognitive, as determined by comparison with a developmental screening tool appropriate for the setting | Severe developmental delay, either motor or cognitive, as determined by comparison with a developmental screening tool appropriate for the setting | Developmental regression, either motor or cognitive, as determined by comparison with a developmental screening tool appropriate for the setting |
| Headache | Symptoms causing no or minimal interference with usual social & functional activities | Symptoms causing greater than minimal interference with usual social & functional activities | Symptoms causing inability to perform usual social & functional activities | Symptoms causing inability to perform basic self-care functions OR Hospitalization indicated (other than emergency room visit) OR Headache with significant impairment of alertness or other neurologic function |
| Insomnia | NA | Difficulty sleeping causing greater than minimal interference with usual social & functional activities | Difficulty sleeping causing inability to perform usual social & functional activities | Disabling insomnia causing inability to perform basic self-care functions |
| Neuromuscular weakness (including myopathy & neuropathy) | Asymptomatic with decreased strength on exam OR Minimal muscle weakness causing no or minimal interference with usual social & functional activities | Muscle weakness causing greater than minimal interference with usual social & functional activities | Muscle weakness causing inability to perform usual social & functional activities | Disabling muscle weakness causing inability to perform basic self-care functions OR Respiratory muscle weakness impairing ventilation |

| PARAMETER | GRADE 1 MILD | GRADE 2 MODERATE | GRADE 3 SEVERE | GRADE 4 POTENTIALLY LIFE- THREATENING |
|--|--|---|--|--|
| Neurosensory alteration (including paresthesia and painful neuropathy) | Asymptomatic with sensory alteration on exam or minimal paresthesia causing no or minimal interference with usual social & functional activities | Sensory alteration or paresthesia causing greater than minimal interference with usual social & functional activities | Sensory alteration or paresthesia causing inability to perform usual social & functional activities | Disabling sensory alteration or paresthesia causing inability to perform basic self-care functions |
| Seizure: (new onset) – Adult ≥ 18 years See also Seizure: (known pre-existing seizure disorder) | NA | 1 seizure | 2 – 4 seizures | Seizures of any kind which are prolonged, repetitive (e.g., status epilepticus), or difficult to control (e.g., refractory epilepsy) |
| Seizure: (known pre-existing seizure disorder) – Adult ≥ 18 years For worsening of existing epilepsy the grades should be based on an increase from previous level of control to any of these levels | NA | Increased frequency of pre-existing seizures (non-repetitive) without change in seizure character OR Infrequent break-through seizures while on stable medication in a previously controlled seizure disorder | Change in seizure character from baseline either in duration or quality (e.g., severity or focality) | Seizures of any kind which are prolonged, repetitive (e.g., status epilepticus), or difficult to control (e.g., refractory epilepsy) |
| Seizure – Pediatric <18 years | Seizure, generalized onset with or without secondary generalization, lasting <5 minutes with <24 h post ictal state | Seizure, generalized onset with or without secondary generalization, lasting 5 – 20 minutes with <24 h post ictal state | Seizure, generalized onset with or without secondary generalization, lasting >20 minutes | Seizure, generalized onset with or without secondary generalization, requiring intubation and sedation |

| PARAMETER | GRADE 1 MILD | GRADE 2 MODERATE | GRADE 3 SEVERE | GRADE 4 POTENTIALLY LIFE- THREATENING |
|--|--|---|---|--|
| Syncpe (not associated with a procedure) | NA | Present | NA | NA |
| Vertigo | Vertigo causing no or minimal interference with usual social & functional activities | Vertigo causing greater than minimal interference with usual social & functional activities | Vertigo causing inability to perform usual social & functional activities | Disabling vertigo causing inability to perform basic self-care functions |

| PARAMETER | GRADE 1 MILD | GRADE 2 MODERATE | GRADE 3 SEVERE | GRADE 4 POTENTIALLY LIFE- THREATENING |
|--|--|---|--|--|
| RESPIRATORY | | | | |
| Bronchospasm (acute) | FEV1 or peak flow reduced to 70 – 80% | FEV1 or peak flow 50 – 69% | FEV1 or peak flow 25 – 49% | Cyanosis OR FEV1 or peak flow <25% OR Intubation |
| Dyspnea or respiratory distress | | | | |
| Adult ≥14 years | Dyspnea on exertion with no or minimal interference with usual social & functional activities | Dyspnea on exertion causing greater than minimal interference with usual social & functional activities | Dyspnea at rest causing inability to perform usual social & functional activities | Respiratory failure with ventilatory support indicated |
| Pediatric <14 years | Wheezing OR minimal increase in respiratory rate for age | Nasal flaring OR Intercostal retractions OR Pulse oximetry 90 – 95% | Dyspnea at rest causing inability to perform usual social & functional activities OR Pulse oximetry <90% | Respiratory failure with ventilatory support indicated |
| MUSCULOSKELETAL | | | | |
| Arthralgia See also Arthritis | Joint pain causing no or minimal interference with usual social & functional activities | Joint pain causing greater than minimal interference with usual social & functional activities | Joint pain causing inability to perform usual social & functional activities | Disabling joint pain causing inability to perform basic self-care functions |
| Arthritis See also Arthralgia | Stiffness or joint swelling causing no or minimal interference with usual social & functional activities | Stiffness or joint swelling causing greater than minimal interference with usual social & functional activities | Stiffness or joint swelling causing inability to perform usual social & functional activities | Disabling joint stiffness or swelling causing inability to perform basic self-care functions |

| PARAMETER | GRADE 1 MILD | GRADE 2 MODERATE | GRADE 3 SEVERE | GRADE 4 POTENTIALLY LIFE- THREATENING |
|---|---|--|--|--|
| Bone Mineral Loss | | | | |
| Adult ≥21 years | BMD t-score -2.5 to -1.0 | BMD t-score <-2.5 | Pathological fracture (including loss of vertebral height) | Pathologic fracture causing life-threatening consequences |
| Pediatric <21 years | BMD z-score -2.5 to -1.0 | BMD z-score <-2.5 | Pathological fracture (including loss of vertebral height) | Pathologic fracture causing life-threatening consequences |
| Myalgia (non-injection site) | Muscle pain causing no or minimal interference with usual social & functional activities | Muscle pain causing greater than minimal interference with usual social & functional activities | Muscle pain causing inability to perform usual social & functional activities | Disabling muscle pain causing inability to perform basic self-care functions |
| Osteonecrosis | NA | Asymptomatic with radiographic findings AND No operative intervention indicated | Symptomatic bone pain with radiographic findings OR Operative intervention indicated | Disabling bone pain with radiographic findings causing inability to perform basic self-care functions |
| GENITOURINARY | | | | |
| Cervicitis (symptoms) (For use in studies evaluating topical study agents) For other cervicitis see Infection: Infection (any other than HIV infection) | Symptoms causing no or minimal interference with usual social & functional activities | Symptoms causing greater than minimal interference with usual social & functional activities | Symptoms causing inability to perform usual social & functional activities | Symptoms causing inability to perform basic self-care functions |

| PARAMETER | GRADE 1 MILD | GRADE 2 MODERATE | GRADE 3 SEVERE | GRADE 4 POTENTIALLY LIFE- THREATENING |
|--|--|---|--|--|
| Cervicitis (clinical exam) (For use in studies evaluating topical study agents) For other cervicitis see Infection: Infection (any other than HIV infection) | Minimal cervical abnormalities on examination (erythema, mucopurulent discharge, or friability) OR Epithelial disruption <25% of total surface | Moderate cervical abnormalities on examination (erythema, mucopurulent discharge, or friability) OR Epithelial disruption of 25 – 49% total surface | Severe cervical abnormalities on examination (erythema, mucopurulent discharge, or friability) OR Epithelial disruption 50 – 75% total surface | Epithelial disruption >75% total surface |
| Inter-menstrual bleeding (IMB) | Spotting observed by participant OR Minimal blood observed during clinical or colposcopic examination | Inter-menstrual bleeding not greater in duration or amount than usual menstrual cycle | Inter-menstrual bleeding greater in duration or amount than usual menstrual cycle | Hemorrhage with life-threatening hypotension OR Operative intervention indicated |
| Urinary tract obstruction (e.g., stone) | NA | Signs or symptoms of urinary tract obstruction without hydronephrosis or renal dysfunction | Signs or symptoms of urinary tract obstruction with hydronephrosis or renal dysfunction | Obstruction causing life-threatening consequences |
| Vulvovaginitis (symptoms) (Use in studies evaluating topical study agents) For other vulvovaginitis see Infection: Infection (any other than HIV infection) | Symptoms causing no or minimal interference with usual social & functional activities | Symptoms causing greater than minimal interference with usual social & functional activities | Symptoms causing inability to perform usual social & functional activities | Symptoms causing inability to perform basic self-care functions |

| PARAMETER | GRADE 1 MILD | GRADE 2 MODERATE | GRADE 3 SEVERE | GRADE 4 POTENTIALLY LIFE- THREATENING |
|--|---|--|---|---|
| Vulvovaginitis (clinical exam) (Use in studies evaluating topical study agents) For other vulvovaginitis see Infection: Infection (any other than HIV infection) | Minimal vaginal abnormalities on examination OR Epithelial disruption <25% of total surface | Moderate vaginal abnormalities on examination OR Epithelial disruption of 25 - 49% total surface | Severe vaginal abnormalities on examination OR Epithelial disruption 50 - 75% total surface | Vaginal perforation OR Epithelial disruption >75% total surface |
| OCULAR/VISUAL | | | | |
| Uveitis | Asymptomatic but detectable on exam | Symptomatic anterior uveitis OR Medical intervention indicated | Posterior or pan-uveitis OR Operative intervention indicated | Disabling visual loss in affected eye(s) |
| Visual changes (from baseline) | Visual changes causing no or minimal interference with usual social & functional activities | Visual changes causing greater than minimal interference with usual social & functional activities | Visual changes causing inability to perform usual social & functional activities | Disabling visual loss in affected eye(s) |
| ENDOCRINE/METABOLIC | | | | |
| Abnormal fat accumulation (e.g., back of neck, breasts, abdomen) | Detectable by study participant (or by caregiver for young children and disabled adults) | Detectable on physical exam by health care provider | Disfiguring OR Obvious changes on casual visual inspection | NA |
| Diabetes mellitus | NA | New onset without need to initiate medication OR Modification of current medications to regain glucose control | New onset with initiation of medication indicated OR Diabetes uncontrolled despite treatment modification | Life-threatening consequences (e.g., ketoacidosis, hyperosmolar non-ketotic coma) |

| PARAMETER | GRADE 1 MILD | GRADE 2 MODERATE | GRADE 3 SEVERE | GRADE 4 POTENTIALLY LIFE- THREATENING |
|---|--|--|---|---|
| Gynecomastia | Detectable by study participant or caregiver (for young children and disabled adults) | Detectable on physical exam by health care provider | Disfiguring OR Obvious on casual visual inspection | NA |
| Hyperthyroidism | Asymptomatic | Symptomatic causing greater than minimal interference with usual social & functional activities OR Thyroid suppression therapy indicated | Symptoms causing inability to perform usual social & functional activities OR Uncontrolled despite treatment modification | Life-threatening consequences (e.g., thyroid storm) |
| Hypothyroidism | Asymptomatic | Symptomatic causing greater than minimal interference with usual social & functional activities OR Thyroid replacement therapy indicated | Symptoms causing inability to perform usual social & functional activities OR Uncontrolled despite treatment modification | Life-threatening consequences (e.g., myxedema coma) |
| Lipoatrophy (e.g., fat loss from the face, extremities, buttocks) | Detectable by study participant (or by caregiver for young children and disabled adults) | Detectable on physical exam by health care provider | Disfiguring OR Obvious on casual visual inspection | NA |

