7.1.3. Individual Participant Laboratory Abnormality and Adverse Event Stopping Criteria

Investigators should make every effort to have a discussion with the Medical Monitor before the next dose to help assess if the study intervention should be stopped. Individual participant laboratory abnormality and AE stopping criteria for the study, as follows:

| | |
|---------------|---|
| Adverse Event | 
 Any clinically significant AE deemed to require discontinuation of the IP Any related Grade 3 or any Grade 4 rash Grade 2 rash with evidence of systemic involvement Grade 2 or higher rash with concurrent fever, AST/ALT elevation or eosinophilia prior to the follow up phase will be withdrawn from study intervention Grade 3 or higher allergic reaction Any Grade 3 or higher Psychiatric AE. The investigator will discontinue the participant from the study and arrange for emergency psychiatric evaluation/management; the panel for drugs of abuse will be tested New onset suicidal ideation as clinically diagnosed by the Investigator (in consultation with psychiatry, if needed). The Investigator will discontinue the participant from the study and arrange for emergency specialist psychiatric evaluation/management Any Grade 3 or higher AE related to study medication Any Grade 4 AE or laboratory abnormalities (with the exception of an asymptomatic grade 4 cholesterol, triglyceride or CPK increase) A participant meets the QTcF stopping criteria described in Section 7.1.2 Moderate to severe (as clinically determined by the investigator) COVID-19 infection (suspect, probable, or confirmed using the most recent version of the WHO case definition) |
|---------------|---|

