10.7. Appendix 7: Toxicity Management

Adverse events that occur during the study should be evaluated by the investigator and graded according to the DAIDS toxicity scales (see Section 10.8). Additional information regarding detecting, documenting and reporting AEs and SAEs are available in Section 10.3.

Study drug may be interrupted at the discretion of the investigator and according to the severity of the AE.

No toxicity-related dose reductions of study drugs will be allowed. Guidance is provided below on subject management and study drug interruptions based on the severity of the AE for specific toxicities. All changes in study drug must be accurately recorded in the participant's eCRF.

Grade 1 or Grade 2 Toxicity/Adverse Event

Participants who develop a Grade 1 or Grade 2 AE or toxicity may continue study treatment at the discretion of the investigator. Participants who choose to withdraw from the study due to a Grade 1 or 2 AE should have study withdrawal and follow-up evaluations completed.

Grade 3 Toxicity/Adverse Event

Participants who develop a Grade 3 AE or toxicity should be managed as follows:

If the investigator has compelling evidence that the Grade 3 AE or toxicity has not been caused by study treatment, dosing may continue after discussion with the medical monitor.

Participants who develop a Grade 3 AE or toxicity that the investigator considers related to the study drugs should have study treatment permanently discontinued and be rechecked each week (at minimum) until the resolution of the AE.

Participants with asymptomatic Grade 3 laboratory abnormalities should be investigated for all potential non-drug related causes, and, following discussion with the medical monitor, may continue study drug if the investigator has compelling evidence that the toxicity is not related to study treatment.

Grade 4 Toxicity/Adverse Event

Participants experiencing Grade 4 AEs requiring permanent discontinuation of study treatment should be followed weekly until resolution of the AE and encouraged to complete the withdrawal and follow-up study evaluations as noted above.

Specific Toxicities/Adverse Event Management

General guidelines for the management of specific toxicities that are considered to be related or possibly related to study treatment are provided below.

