Participants who permanently discontinue study treatment for reasons of toxicity should be followed weekly until resolution of the AE and encouraged to complete the withdrawal and Follow-up study evaluations (see Section 1.3).

Liver Chemistry Stopping and Follow-up Criteria

Liver chemistry threshold stopping criteria have been designed to assure participant safety and to evaluate liver event aetiology during administration of study drug and the follow-up period. For a complete listing of stopping and follow-up criteria refer to Section 7.1.1 and Section 10.6.

Hypertriglyceridemia/Hypercholesterolemia

Samples for lipid measurements must be obtained in a fasted state according to the SoA (see Section 1.3). Participants who experience asymptomatic triglyceride or cholesterol elevations may continue to receive study drug.

Creatine Phosphokinase (CPK) Elevation

A Grade 3 or higher elevation in CPK should result in a repeat assessment within 2 to 4 weeks to ensure the result is transient or due to exercise and will not require a change in study treatment. A history regarding use of drugs known to cause increase of CPK (such as statins), physical activity or exercise preceding the CPK evaluation should be obtained. Grade 4 elevations in CPK should have a repeat assessment after the subject has abstained from exercise for >24 h. For persistent Grade 4 CPK elevations that are considered possibly or probably related to the study drugs, study treatment should be discontinued and the subject withdrawn from the study

RASH**Grade 1 rash**

Participants with an isolated Grade 1 rash may continue study drug at the Investigator's discretion. The participant should be advised to contact the Investigator immediately if there is any worsening of the rash, if any systemic signs or symptoms appear, or if mucosal involvement develops.

Grade 2 rash

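### The 2-to-4-week CPK recheck falls after 7-day dosing has ended, and a related Grade 4 CPK rise is handled less strictly than a related Grade 3 rise

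*Protocol*

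**What the plan says.** The CPK paragraph of Protocol 10.7 (Appendix 7) states "A Grade 3 or higher elevation in CPK should result in a repeat assessment within 2 to 4 weeks". The purpose it gives is to show that the rise is transient or exercise-related and that treatment can stay as it is. It then adds a separate step, "Grade 4 elevations in CPK should have a repeat assessment after the subject has abstained from exercise for >24 h", and one stopping rule, "For persistent Grade 4 CPK elevations that are considered possibly or probably related to the study drugs, study treatment should be discontinued". The paragraph belongs to guidance for "specific toxicities that are considered to be related or possibly related to study treatment".

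The general Grade 3 text of 10.7 covers any Grade 3 adverse event or toxicity. If the investigator considers it related, the participant "should have study treatment permanently discontinued and be rechecked each week (at minimum) until the resolution of the AE". A participant with an asymptomatic Grade 3 laboratory abnormality "may continue study drug if the investigator has compelling evidence that the toxicity is not related to study treatment", after discussion with the medical monitor.

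Protocol 7.1.3 lists "Any Grade 3 or higher AE related to study medication" as a stopping criterion. A separate line stops any Grade 4 adverse event or laboratory abnormality, "with the exception of an asymptomatic grade 4 cholesterol, triglyceride or CPK increase". No text says which of these provisions takes precedence.

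**The concern.** The recheck is meant partly to settle whether dosing may go on, but in a 7-day course the answer arrives after the last dose. Holding a dose while waiting is not a clean alternative. Section 10.7 lets the investigator interrupt study drug, but 7.1.4 (partly redacted) requires withdrawal after a missed dose on Days 1 to 7.

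The stopping rules also look out of order by grade: on a plain reading, a related Grade 3 rise can end treatment sooner than a related Grade 4 rise.

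At stake are safety decisions for a daily-dose participant with a related Grade 3 or 4 result reported before the last dose. The rule applied also decides whether the case counts as an adverse event leading to discontinuation through Day 8, which is a secondary endpoint (3.1). Under 4.1, a participant who stops for meeting stopping criteria is not replaced.

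**Working it through.** **Inputs.** Dosing Days 1 to 7, follow-up to Day 25, screening 7 to 14 days with a maximum of 28 (Protocol 4.1). Chemistry at screening and on Days 1, 3/4, 5/6, 7, 8, 14, 21 and 25 (Schedule of Activities). CPK is in the chemistry panel (10.2, Table 10). Recheck interval 14 to 28 days (10.7).

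**The plan's own timeline.** 7 + 7 + 18 = 32 days and 28 + 7 + 18 = 53 days, which matches the stated 32 to 53. Follow-up is 25 − 7 = 18 days.

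**Recheck window.** Opens on sample day + 14 and closes on sample day + 28.

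| Sample day | Window (Days) | Opens after last dose (Day 7) by |
|---|---|---|
| 1 (pre-dose) | 15–29 | 8 days |
| 3 | 17–31 | 10 |
| 4 | 18–32 | 11 |
| 5 | 19–33 | 12 |
| 6 | 20–34 | 13 |
| 7 | 21–35 | 14 |
| 8 | 22–36 | 15 |
| 14 | 28–42 | 21 |
| 21 | 35–49 | 28 |
| 25 | 39–53 | 32 |

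No sample from Day 1 on has a window that opens by Day 7. From the Day 14 sample on, the window opens after Day 25. Screening is the exception: a sample taken 14 days before Day 1 has a window of Days 1 to 15, which overlaps dosing. A CPK rise at screening is not exclusionary (5.2, criterion 24), but it cannot be drug-related.

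**The separate Grade 4 repeat.** It can fall within dosing. A Day 3 sample could be repeated from Day 4 or 5. No outer time limit is given.

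**What an earlier recheck could do.** Laboratory turnaround is not stated. As an illustration, assume a result is back T = 1 to 3 days after sampling on day d, before that day's dose. Doses still to come = 8 − d − T, not below 0.

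- Visit 3: d = 3 gives 4, 3, 2; d = 4 gives 3, 2, 1. Range 1 to 4.
- Visit 4: d = 5 gives 2, 1, 0; d = 6 gives 1, 0, 0. Range 0 to 2.
- Day 7: 0.

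So a visit 3 finding could still affect 1 to 4 doses, and its repeat at visit 4 could affect 0 to 2. The 2-to-4-week recheck affects 0.

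**Stopping rules for a related CPK rise.**

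| Rise | 10.7 general text | 10.7 CPK paragraph | 7.1.3 |
|---|---|---|---|
| Grade 3 | Stop, recheck at least weekly | Recheck at 2 to 4 weeks; says neither stop nor continue | Stop if recorded as an adverse event |
| Grade 4, asymptomatic | Follow-up only; no separate decision rule | Repeat after >24 h; stop only if persistent | Exempt from the Grade 4 line; stop under the related Grade 3+ line if an adverse event |
| Grade 4, symptomatic | As above | As above; symptoms not mentioned | Stop |

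At Grade 3 the provisions that give a rule agree. At Grade 4 they do not: once a related rise is recorded as an adverse event, 7.1.3 stops at once and the CPK paragraph waits for persistence.

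**Reach.** SAP 4.7 (footnote) records that the interim has taken place. It required all Part 1 participants to have completed Day 8, so Part 1 dosing is over. SAP 1.2 plans 6 + 1 = 7 participants in Part 2, with the regimen redacted. A change made now can therefore reach 0 to 7 participants for dosing purposes, at most 6 of them on active drug. One discontinuation in a cohort of 6 is 1/6 = 17%; that is the size of a single event, not a forecast.

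**The case against.** Monitoring does not depend on the CPK paragraph. Section 8.3.4 asks for clinically significant abnormal tests to be repeated until they return to normal or baseline, with no two-week delay. Section 8 allows unscheduled safety samples, 10.2 allows additional tests at any time, and CPK is measured again on Days 3/4, 5/6, 7 and 8. The 2-to-4-week recheck also keeps a follow-up use: windows from Day 3 to Day 7 samples include the Day 21 and Day 25 visits. This stands and limits the harm. It does not rescue the part of the stated purpose that concerns treatment. A reader might infer that CPK goes unobserved for two weeks; the schedule shows otherwise.

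A reader might also infer that the protocol has no rule for a related Grade 3 rise, or tells investigators to keep dosing. The documents do not support either. The general text of 10.7 and 7.1.3 both stop a related Grade 3 event, and the CPK paragraph never says to continue. What is missing is a cross-reference.

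At Grade 4 the conflict is narrow. A laboratory abnormality is an adverse event only if the investigator judges it clinically significant (8.3.4, 10.3.1). An asymptomatic Grade 4 rise judged not significant is exempt under 7.1.3, and 10.7 then adds a stop if it is persistent and related; those two rules fit together. Section 7.1.3 also expects every effort to discuss with the medical monitor before the next dose. The conflict remains for a related Grade 4 rise recorded as an adverse event.

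**Conclusion.** The timing point holds: for every sample from Day 1 on, the 2-to-4-week recheck comes at least 8 days after the last dose and cannot show that dosing may stay unchanged. The gap is mainly at Grade 3, because Grade 4 has its own earlier repeat. The ordering point holds at Grade 4 only: a related Grade 4 rise can be kept on drug pending a repeat when a related Grade 3 rise would already have stopped, and this contradicts 7.1.3 if the rise is an adverse event.

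This is a minor, desirable correction. It matters only for a daily-dose participant with a related Grade 3 or higher result reported before the last dose. No CPK rate is given, and the first-in-human study reported no clinically significant chemistry changes on drug (2.2.1.1), so no expected number of cases can be stated. The day counts rest on the documents alone; the doses-affected ranges rest on the assumed 1-to-3-day turnaround.

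**What to change.** In the CPK paragraph of 10.7, replace the 2-to-4-week interval with: *at the next scheduled chemistry visit, or by an unscheduled sample before the next dose where feasible, then at least weekly through Day 25 or until resolution*. State that a related Grade 3 CPK rise follows the general Grade 3 rule of 10.7, and that a related Grade 4 rise is handled no less strictly. Use the same wording in 7.1.3, including its asymptomatic Grade 4 exemption. The alternative of exempting asymptomatic related rises at both grades would also be consistent, but it would loosen the existing Grade 3 stop.

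Cost: a protocol amendment, which under 10.1.1 needs ethics and health authority approval if substantial; occasional unscheduled samples, with a local result allowed by 8.3.4 when the central one is late; and possibly one more unreplaced discontinuation. The scheduled visits already supply most rechecks. Strenuous exercise is barred on Days 1 to 8 (5.3.3), so the exercise condition should rarely delay a Grade 4 repeat.
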